3.5 Matched control group

A number of the study's objectives and associated outcome measures will require a control group for comparison. These objectives include:

- To assess the cost-effectiveness of delivering Fresh Start;
- To assess the safety of Fresh Start; and
- To assess the impact of Fresh Start on clinical outcomes.

This study will create a matched control group using propensity score matching (PSM),⁹ a quasi-experimental method used to mimic the characteristics of a randomised control trial that has been shown to reduce biases.¹⁰ PSM uses statistical techniques to construct an artificial control group by matching each study participant with a non-treated participant of similar characteristics. PSM computes the probability that a person would enrol in a program based on pre-defined characteristics, giving a 'propensity score'.

The propensity score for the study will be based on the following characteristics:

- Age
- Gender
- Risk category (see inclusion criteria)
- Geographical proximity
- Social deprivation index (by practice)

Each individual in the matched control group will be identified within one month of the index case.

Imperial College London

The matched control group will be identified using NWL's Whole of Systems Integrated Care (WSIC) database. WSIC links provider data from four acute, two mental health and two community Trusts across eight CCGs, social care data from eight boroughs and 380 GP practices to generate an integrated care record.

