3.11 Data analysis

The research team will not have access to any personal or identifiable patient data as part of the project. Data will be de-identified before being transferred to WSIC's de-identified data (DID) environment and made available to approved researchers. Any data extracted from the secure environment after analysis by the research team will be at an aggregate level only.

All outcomes will be reported using descriptive statistics with tables and graphical presentations of findings. Continuous variables will be presented as means and standard deviations if normally distributed, and as medians and inter-quartile ranges for skewed data, whilst categorical variables will be presented as frequencies and percentages.

To assess the pre-test/post-test change on clinical outcomes the appropriate generalized mixed model approach will be used to account for repeated measurements and clustering of GP practices and including important covariates in the model.

To create a matched control group from NWL's WSIC database, a 1:1 propensity score matching (PSM) analysis will be performed using age, gender, risk category, geographical proximity and social deprivation index as matching variables. R statistical software will be used for estimating PS by logistic regression and for balance and sensitivity checks.

Comparisons with the control group for clinical outcomes will be exploratory and differences with 95% CI will be reported using the appropriate generalized mixed model.

Interviews conducted with participants and healthcare professionals will be analysed using NVivo, where responses will undergo thematic analysis using an inductive approach to derive key themes.

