3.12 Data privacy and security

The research team will not have access to any personal or identifiable patient data as part of the project. Data will be de-identified before being transferred to WSIC's de-identified data (DID) environment and made available to approved researchers. Any data extracted from the secure environment after analysis by the research team will be at an aggregate level only.

A single WSIC analyst who is responsible for flagging patients in the matched control group will have access to the personal identifiable data (PID) environment. This WSIC analyst has

a substantive contract with the data controller and is authorised to execute the flagging in the PID.

The WSIC dataset is a PID hosted by UKCloud in a secure cloud-based environment, which is ISO27017 certified. This is an Identifiable data set which supports clinicians and health care professionals to provide joined-up care, decision-support and workflow automation. This information feeds into a wide range of bespoke assets for example clinical facing WSIC dashboards and the Health Information Exchange (HIE) for use by clinicians, and the Care Information Exchange (CIE) and coordinate my care for use by citizens.

Discover Dataset is de-identified dataset hosted in a secure Azure environment and to be hosted by IBM in a new Trusted Research Environment (TRE). This depersonalised data set is for quality improvement planning and research, it is controlled by NWL data controllers, and access to it is mediated by the NWL Data Access Committee. It is accessible via Discover-NOW Health Data Research Hub for Real World Evidence through their data scientists specialists hosted by Imperial College Health Partners (ICHP) and IG committee-approved analysts to conduct research within the safe environment.

Data collected on the Huma platform is hosted in the UK by Google Cloud Platform (GCP) who manage all physical servers, resources and networking hardware to enable all business logic and higher-level services. All communications are secured by TLS. Huma follows NIST approved encryption techniques for encrypting data-at-rest. Huma's cloud provider provides Key Management Services (KMS) for data storage services using an encryption key. Key rotation is performed. Huma practises the concept of least-privileged permissions for services. Huma also conforms to the following accreditations and standards:

- NHS Data Security and Protection Toolkit certification (organisational code: YGMA8)

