7.1.2. Propensity Score Matching

For the primary cost-benefit comparison and secondary safety and efficacy comparisons, study data will be compared against a matched-control group established via propensity score matching. This is achieved by deriving a propensity score for each enrolled patient based on the following characteristics:

- Age
- Gender
- Geographical proximity
- Social deprivation index (by practice)

- Ethnicity

Using the above categories, taking 'arm' as the dependent variable, logistic regression using a generalised logit model will be used to generate the estimated propensity scores. Scores are also applied to a control 'arm' taken from the WSIC database as section 5.2.2 with everyone in the matched control identified within one month of the index case. The scores are then used to 'pair-up' patients within both groups, patients will be matched on a 1:1 basis without replacement.

Scores are to be calculated using PSOCORE in STATA. Matching is to be carried out using PSMATCH2 (or a suitable alternative). Balancing on matching variables is to be checked once matching is completed using PSTEST. If any variable is found to be unbalanced the matching is repeated, either adjusting the matching method or caliper used.

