7.4. Patient Demographics & Baseline Readings

Tables summarising demographics are to be produced for both the FreshStart and propensity-matched groups. Additional output will be produced dichotomising the FreshStart group into 2 subgroups; those that used the HUMA device, and those that did not.

Demographics will cover Age, Gender, Ethnicity, Deprivation Score & Location

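### Deprivation enters the propensity score only as a practice value, so matching cannot correct for deprivation-related volunteering within a practice, and the planned balance check would not detect it

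*Protocol*

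**What the plan says.** Protocol 3.5 describes the propensity score as the probability that a person enrols. Its deprivation term is "Social deprivation index (by practice", and SAP 7.1.2 repeats that term. Protocol 3.11 lists "geographical proximity and social deprivation index as matching variables" and gives no level. No other socioeconomic variable is in the score. Age and gender are patient-level terms in both documents. The protocol adds "Risk category (see inclusion criteria", while the SAP list has ethnicity and no risk category.

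Under SAP 7.1.2, "patients will be matched on a 1:1 basis without replacement". Then: "Balancing on matching variables is to be checked once matching is completed using PSTEST". The only consequence is: "If any variable is found to be unbalanced the matching is repeated, either adjusting the matching method or caliper used".

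Deprivation appears in two other places, both without a level:
- SAP 7.4 says "Demographics will cover Age, Gender, Ethnicity, Deprivation Score & Location", and Template 1 shows deprivation in deciles. No action is tied to that table.
- The models in SAP 7.5.5 and 7.6.2 include a social deprivation index as a covariate.

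**The concern.** Enrolment is decided patient by patient. Protocol 3.3 expects 20% of the 1,500 patients identified to enrol. Section 3.7 describes a phone call and requires the Huma app to be downloaded, and section 4.4 excludes patients without a smartphone. It is plausible that deprivation influences who says yes. A practice value cannot carry that information.

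If less deprived patients volunteer more readily, they would be compared with more deprived controls, and part of any difference in appointments, cost or admissions would be credited to the service. The check meant to guard against this would look at the practice value, find it balanced and trigger no re-matching.

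**Working it through.** The plan gives no figure for balance or for uptake by deprivation, so there is none to reproduce. The check asks what a practice-level term can do and how large the gap could be.

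**1. What the term can do.** A practice value adds the same constant to the logit of every patient in that practice. Within a practice, scores can differ only through age, gender, ethnicity (SAP) or risk category (protocol), and through geographical proximity if that varies between patients. Proximity is not defined.

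**2. Hand calculation.** Let patient deprivation have variance 1, with a share ρ between practices. Let OR be the odds ratio of enrolling per within-practice SD of deprivation. For a normal variable with equal variances, ln(OR) is the difference in means between enrollers and non-enrollers in within-practice SDs. Ignoring the other matching variables:
- Controls from the same practices: difference ≈ ln(OR) × √(1 − ρ).
- Controls from other practices: multiply by 1 − 0.20 = 0.80, because the comparison is with all eligible patients and not only with those who did not enrol.

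At OR 0.7 and ρ = 0.2: ln(0.7) = −0.357 and √0.8 = 0.894. This gives −0.319 (same practices) and −0.255 (other practices).

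**3. Simulation.** From the documents: 10 participating practices, 1,500/10 = 150 eligible patients in each, about 20% enrolment, 380 practices in WSIC, 1:1 matching without replacement. Assumed: OR, ρ, and a latent correlation of 0.3 between ethnicity and within-practice deprivation. The score used age, sex, ethnicity and practice-mean deprivation, with nearest-neighbour matching, no caliper and 8 replicates per setting. Proximity was not simulated. Entries are standardised differences in patient deprivation after matching; negative means the Fresh Start group is less deprived.

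| OR per SD | Other practices, ρ 0.2 | Other practices, ρ 0.5 | Same practices, ρ 0.2 | Same practices, ρ 0.5 |
|---|---|---|---|---|
| 1.0 | −0.02 | −0.02 | −0.03 | 0.00 |
| 0.9 | −0.11 | −0.03 | −0.11 | −0.05 |
| 0.8 | −0.09 | −0.11 | −0.15 | −0.15 |
| 0.7 | −0.22 | −0.20 | −0.31 | −0.21 |
| 0.5 | −0.39 | −0.35 | −0.55 | −0.47 |

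The practice index itself was within ±0.04 in every setting, so the planned check would pass throughout. With about 300 pairs, one replicate has a standard error near √(2/300) = 0.082, and the mean of 8 has 0.082/√8 = 0.029. The small values at OR 1.0, and the overlap between 0.9 and 0.8, are within that noise.

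**4. Does ethnicity stand in for deprivation?** At OR 0.7, ρ = 0.2 and controls from other practices, raising the correlation from 0.3 to 0.6 to 0.9 gave −0.22, −0.26 and −0.14. Matching on ethnicity removes little unless the correlation is very high.

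**5. Which comparisons depend on the match.**
- Appointments and cost (SAP 7.5.5, a primary objective): adjusted for sex, age, deprivation index and practice clustering; no baseline or prior use.
- Safety composite (SAP 7.6.1): difference in numbers of patients with a 95% CI; no covariates stated.
- SBP and time-in-range (SAP 7.6.2): no baseline term in the main models.
- HbA1c, lipids and weight (SAP 7.6.2): adjusted for each patient's baseline.
- Uptake and usability: no control group.

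**6. Effect on a rate.** If event rates rise by 10-30% per SD of deprivation (an assumption), the OR 0.7 band of 0.20-0.31 gives rate ratios from 1.1^0.20 = 1.02 to 1.3^0.31 = 1.08. That is an apparent advantage of about 2-8% for Fresh Start.

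**The case against.** The best defence is that other parts of the plan may cover the gap. If the covariate in SAP 7.5.5 and 7.6.2 is a patient-level index, the models adjust for it; if the demographics table uses one, an imbalance would be visible. A reader might infer that both use the practice value, because that is the only level either document gives. The documents are silent, so it cannot be said that adjustment fails. Even on the favourable reading, no re-matching follows from the table and the safety composite has no stated adjustment.

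Three other strong readings are not supported:
- That matching does nothing about who volunteers. Age, gender, and ethnicity or risk category are patient-level; the gap concerns deprivation.
- That patient-level deprivation will be imbalanced. No uptake data by deprivation are given, and without selection the difference is about 0.
- That the practice index merely repeats geographical proximity. Proximity is undefined, and if based on residence it could partly capture area deprivation.

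The effect may also be smaller than the study's own noise. With 300 per group and an assumed mean of 2 to 5 appointments, a simple Poisson 95% CI on the rate ratio has a half-width on the log scale of 1.96 × √(2/600) = 0.11 to 1.96 × √(2/1,500) = 0.07, roughly ±7-12%, before clustering or overdispersion. The safety and clinical comparisons are declared exploratory. This limits the weight of the point but does not remove it: cost-effectiveness is a primary objective, and confounding of this kind is not reflected in the interval.

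**Conclusion.** The point holds in a limited form. The practice-level term cannot correct for deprivation-related selection within a practice, and the specified check cannot detect what is left. Whether an imbalance arises, in which direction and how large, depends on assumptions the documents do not supply: the enrolment odds ratio, the between-practice share of variance and the correlation of deprivation with the other matching variables. Over the settings tried, the residual difference runs from about 0 to 0.55 SD and reaches 0.20 or more only at an odds ratio of 0.7 or stronger.

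The appointment and cost comparisons and the safety composite are most exposed. A reader might take HbA1c to be equally exposed; its baseline adjustment makes that unlikely. The change is worth making because it is cheap and replaces a stated method with a better one.

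**What to change.** In protocol 3.5 and SAP 7.1.2, replace the practice-level index with the deprivation decile of the patient's area of residence, where WSIC holds it. The documents do not say whether it does, so confirm this first. Use that one variable in the score, the PSTEST check, the demographics table (SAP 7.4) and the deprivation covariate in SAP 7.5.5 and 7.6.2, and state its level in each place.

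The decile can be attached before de-identification. Protocol 3.12 already provides that the WSIC analyst responsible for "flagging patients in the matched control group will have access to the personal identifiable data (PID) environment". That authorisation covers flagging, so attaching a variable is a small added task to be approved.

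If residence is not held, keep the practice value, say so in all four places, and report within-practice selection on deprivation as an uncorrected limitation.

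Cost: one derived variable, the analyst's extra task, and wording changes to both protocol and SAP. Some patients will lack a decile, so the SAP should state how they are handled. An area index is still not an individual measure, so selection within areas remains uncorrected.

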3.6 Outcome measures

Primary objective	Outcome measure	Where is it recorded?	How often is it measured?	Compare with control?
To assess the feasibility of uptake amongst people with 'high risk' or 'very high risk' type 2 diabetes .	Patients offered Fresh Start vs. enrolled	EPR	Once	No
	Patients enrolled vs. collecting remote monitoring devices	EPR	Once	No
	Patients enrolled vs. downloading Huma app	Huma	Once	No
To assess the usability of Fresh Start amongst people with 'high risk' or 'very high risk' type 2 diabetes .	Number of VGCS attended	EPR	Every 4 weeks	No
	Number of Fresh Start emails opened	KD	Twice weekly	No
	Number of blood glucose measurements recorded	Huma	Daily	No
	Number of blood pressure measurements recorded	Huma	Daily	No
	Number of weight measurements recorded	Huma	Monthly	No
	Number of Diabetes Distress Scale measurements recorded	Huma	Monthly	No
To assess the usability of Fresh Start amongst HCPs .	System Usability Scale (SUS ¹¹) questionnaire	Online survey	Once (at 12 weeks)	No
To assess the acceptability of Fresh Start amongst people with 'high risk' or 'very high risk' type 2 diabetes .	Interviews with patients (x10)	Interview	At 12 weeks	No

To assess the acceptability of Fresh Start amongst HCPs .	Interviews with healthcare professionals (HCPs, x10)	Interview	After intervention period	No
To assess the cost-effectiveness of delivering Fresh Start.	Number of primary care appointments per patient	EPR	Data extracted from EPR	Yes
	Cost per appointment per patient	EPR	Data extracted from EPR	Yes
	Cost of equipment per patient	Huma	N/A	No
Secondary objective (Exploratory)*	Outcome measure			
To assess the safety of Fresh Start.	Number of deaths	EPR	Data extracted from EPR	Yes
	Number of emergency department admissions	WSIC	Data extracted from WSIC	Yes
	Number of hospital admissions	WSIC	Data extracted from WSIC	Yes
To assess the impact of Fresh Start on clinical outcomes .	HbA1c	EPR	Baseline, 12 weeks, 6 months	Yes
	Lipids , incl. LDL and non-HDL cholesterol	EPR	Baseline, 12 weeks, 6 months	Yes
	Weight	EPR	Baseline, 12 weeks, 6 months	Yes
	Diabetes Distress Scale score (DDS ¹²)	Huma	Monthly during service (and at 6 month follow-up appt.)	No
	Blood glucose time-in-range	Huma	Daily	Yes
	Systolic blood pressure (SBP)	Huma	Daily	Yes

**Note: Secondary objectives are exploratory only and will not be demonstrated to a level of statistical significance.*

3.7 Study procedures

This section provides detail on the procedures for delivering Fresh Start and data collection. Standard operating procedure (SOP) documents that go into greater detail have been developed for staff at primary care practices who will be delivering Fresh Start. These include SOPs for practice nurses (PNs), healthcare assistants (HCAs), and administrative staff. A training document has also been developed for participating primary care practices.

The below are the main steps involved to deliver Fresh Start. A high-level overview of study procedures is also provided at Appendix 2.

- Patient search
- Outreach, qualification and booking
- Onboarding
- Fresh Start educational emails
- Huma app, devices and clinician dashboard
- Video group consultations (VGCs)
- Discharge, repeat, or MDT escalation
- Interviews with patients and healthcare professionals
- Online System Usability Scale (SUS) survey

Patient search

EPR searches have been constructed based on the inclusion criteria for this study (see Section 4.3). This search will be run by administrative staff at participating primary care practices. Patients will then be invited to participate in the program.

Staff actions at primary care practice:

- Open practice management system and run report search
- Sense-check list of patients against risk stratification criteria
- Mark exported patients to receive outreach invitation to service

Outreach, qualification and booking

Outreach will involve a 10-minute initial conversation with patients identified in the search to speak to them about how Fresh Start may help them, find out if they are able to participate, and, if interested, book them onto the required appointments to start on Fresh Start. The participant must be able to download the Huma App to their smartphone or tablet.

Staff actions at primary care practice:

- Phone patients on the outreach list
- Qualify if patients are eligible for service
- Organise device collection from the practice
- Book patient onto onboarding appointment
- Keep track of the uptake of Fresh Start
- Book patient for **baseline measurements**, which will include:
 - HbA1c
 - Lipid panel
 - Weight

Onboarding

Imperial College London

A 30-45 minute onboarding appointment will be completed by a practice nurse (PN), healthcare assistant (HCA) or a member of the administrative staff from the participant's primary care practice (at the discretion of the participating practice). The onboarding appointment can be completed via Microsoft Teams or face-to-face (at the discretion of the participant/primary care practice). The onboarding appointment will be used to explain the Huma app, video group consultations (VGCs), and the educational emails from Fresh Start. An onboarding guide and associated script has been developed to support the onboarding process.

Staff actions at primary care practice:

[figure not shown]
- Run one-to-one appointment via Microsoft Teams or a phone call
- Explain how to download and use Huma app & devices
- Book onto VGCs (x3)
- Sign up for Fresh Start emails

Fresh Start educational emails

Patients will be instructed to sign up for Fresh Start educational emails during the onboarding appointment. These emails will be twice-weekly and will ensure patients get supportive information and education on how to improve their type 2 diabetes.

Staff actions at primary care practice:

- Sign patients up to first two Fresh Start emails in onboarding call
- Sign patients up to full Fresh Start campaign in first VGC

Huma app, devices and Clinician Dashboard

The Huma app will enable participants to report their own clinical metrics, feelings, goals and behaviour activities (e.g. photos of food). At the onboarding appointment, participants will be instructed how to download the Huma app from the App Store (for iPhone users) or from the Google Play Store (for all other smartphones). Participants will also be shown how to use their blood pressure cuff and glucometer device, walked through the Diabetes Distress Scale questionnaire, and shown how to set goals and actions in the Huma app.

Imperial College London

[figure not shown]
Participants will be asked to enter results from their first measurements into the Huma app. The HCP who is running the onboarding appointment will check whether results have appeared on the Huma clinician dashboard. If data has not appeared HCPs are advised to contact Huma at [contact].

Huma will also provide a “Clinician Dashboard” to review patient reported data to inform care decisions. The Huma Clinician Dashboard will be used to monitor the blood pressure and blood glucose measurements of participants as they are entered into the Huma app. A HCA at each practice will review the Huma clinician dashboard and escalate any urgent readings to the GP. Data from the dashboard will be provided to PNs in advance of VGCs and will be used to trigger non-urgent care protocols before and after VGC sessions.

[figure not shown]
Staff actions at primary care practice:

- Review Huma Clinician Dashboard daily
- Escalate to GPs when there has been an urgent reading

Patient iPhone and Android app

Clinician Dashboard

Patient Remote Monitoring Devices

- Blood pressure cuff
- Blood glucometer, strips and lances
- Digital scales

Video group consultations (VGCs)

VGCs will be booked and the process for VGCs explained during onboarding. Participants will be booked onto their first VGC approximately one week from the date of the onboarding session, with the second and third booked at four week intervals. Reminder emails containing the Microsoft Teams link to join the session will also be set up during this session. Each VGC will last for 1 hour and 15 minutes in total.

Staff actions at primary care practice **before each VGC**:

- Open Huma Clinician Dashboard patient template side-by-side and manually port patient-reported data from the Huma app into the EPR as follows for patients due to attend VGC session
 - 1 x latest blood pressure reading
 - 1 x latest blood glucose

Imperial College London

[figure not shown]
- 1 x latest Diabetes Distress Score
- 1 x latest weight (BMI automatically calculated)
- Average daily step count for the last week (total for the week / 7)
- Open VGC Discussion Board slide and populate using EPR data
 - Blood pressure – latest reading
 - Blood glucose – latest reading
 - DDS – latest reading
 - BMI – latest reading
 - Average daily step count for the last week (total for the week / 7)
- Review food pictures in Huma dashboard
 - Decide whether to discuss food pictures for that patient on VGC session

Staff actions at primary care practice **during each VGC**:

- Set-up Teams meeting and troubleshoot potential problems with participants (15mins before session start time)
- Take consent
- Share link for Fresh Start emails
- Introductions and theme (video played – 10/15 slides talked to)
- Answer questions in the chat
- Review VGC Discussion Board (see Appendix 3 for example)
 - Speak with each patient one-by-one
 - Set actions for each person

Staff actions at primary care practice **after each VGC**:

- Review VGC Discussion Board and notes from VGC session
- Discuss each patient and possible clinical protocols to apply (e.g. medication, footcare, mental health, renal etc.)
- Make changes to care plan in practice management system
- Refer or book one-to-one appointments with patients (as required)

3 x 1h15m sessions

Huma app data is used to inform and structure conversations with patients

- 6-10 patients
- 1 facilitator
- 1 clinician

Discharge, Repeat or MDT Escalation

At 12 weeks each participant will be formally reviewed and decisions can be made for their future care-plan.

Staff actions at primary care practice:

- Review patient's progress
- Decide whether to discharge patient, repeat them for another 12 weeks on Fresh Start, or escalate them to MDT
- Complete **12-week measurements**, including:
 - HbA1c
 - Lipid panel
 - Weight

Interviews with patients and HCPs.

After the intervention period, interviews will be conducted with 10 people with type 2 diabetes who have participated in Fresh Start and with 10 healthcare professionals from participating primary care practices who have delivered Fresh Start.

Online System Usability Scale (SUS) survey

After the intervention period, the SUS will be distributed via email to all healthcare professionals at participating primary care practices. The SUS is a reliable tool for measuring the usability of a system or service. It consists of a 10-item questionnaire with five response options via a Likert scale, ranging from 'Strongly agree' to 'Strongly disagree'.

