3.8 Training

The aim of the T2DEx training is to equip clinicians and practice staff with sufficient understanding of Fresh Start's objectives and operations to deliver it autonomously at their respective sites. The training will be divided **into three sessions lasting approximately 1.5 hours each**. These sessions will be led by a member of the ICHP team or a clinical implementation role funded through NHSX.

Training sessions will be run via Microsoft Teams using training slide decks that has been created by ICHP. The slide decks form part of the virtual resource pack hosted in Teams, which includes all materials required for Fresh Start delivery. The trainer will walk the attendees through the slide deck, allowing time for questions during the session and at the end. Attendees will receive a feedback form at the end of each session to record their feedback on the training. After each session the trainer will share a copy of the deck with all attendees and invite the attendees to send any questions.

- **The first session** will provide an introduction to the Fresh Start objectives and an overview of all the Fresh Start components. Staff tasked with delivering Fresh Start should attend the full session. This will likely include PNs (practice nurses), healthcare assistants (HCAs), and administrative staff. General practitioners (GPs) or advanced nurse practitioners (ANPs) involved with running the VGCs should also attend the full session. It is recommended that other staff attend the first 15 minutes of this session if they will assume responsibility for any Fresh Start components when their colleagues are absent or on annual leave. At the end of the first session, attendees will be shown the virtual resource pack in Teams. The aim is to show the attendees a summary of the resource pack materials and the location of the materials they will require for their role in Fresh Start. All attendees should be given access to

the resource pack to review and the opportunity to contact the training team with questions.

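### The System Usability Scale goes to every healthcare professional at a participating practice, so replies from staff who never used Fresh Start can enter the only outcome for protocol primary objective 3, and nothing described would separate them.

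*Protocol*

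**What the plan says.** The outcome table in Protocol 3.6 lists, as a primary objective, "To assess the usability of Fresh Start amongst HCPs". Its single outcome measure is the SUS, collected once by online survey. In the numbered list in Protocol section 2 this is primary objective 3.

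Protocol 3.7 sets the recipients: after the intervention period, "the SUS will be distributed via email to all healthcare professionals at participating primary care practices". It describes the SUS as a 10-item questionnaire with five response options that measures the usability of a system or service. The paragraph immediately before it recruits a narrower group for interview: "10 healthcare professionals from participating primary care practices who have delivered Fresh Start".

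Three places bear on who actually uses the service:

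- Dashboard monitoring (Protocol 3.7): "A HCA at each practice will review the Huma clinician dashboard".
- Video group consultations (Protocol 3.7): one facilitator and one clinician per session.
- Training (Protocol 3.8): "Staff tasked with delivering Fresh Start should attend the full session". Of the remainder it says: "It is recommended that other staff attend the first 15 minutes of this session if they will assume responsibility for any Fresh Start components", the occasion being a colleague's absence or leave.

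Protocol 3.11 promises descriptive statistics for all outcomes and says nothing specific to the SUS. SAP 4.1 lists five primary objectives, and HCP usability is not among them. SAP 6.1, 6.2, 7.2 and 7.5 and the table list in SAP Appendix 1 contain no SUS outcome or analysis. The scale appears in the SAP only in the list of abbreviations.

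**The concern.** A usability scale asks respondents to rate something they have operated. A GP or nurse at a participating practice who took no part in Fresh Start has no experience to rate, yet is on the mailing list. If such people answer, the reported score is a weighted average of users' ratings and uninformed opinion, with unknown weights.

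The protocol draws the relevant line for the interviews, which serve acceptability, but not for the SUS, where hands-on use matters at least as much. The survey is administered once and is the objective's only measure, so exposure that is not recorded at that time could be recovered only by contacting respondents again. Any response rate that is reported would also count, in its denominator, people with nothing to rate.

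**Working it through.** The documents give no SUS target, standard deviation, number of staff or expected number of replies, so there is no planned figure to reproduce. The check is mainly a comparison of text.

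**1. Does anything limit the recipients to users?** Protocol 3.7 says all healthcare professionals at participating practices. No restriction appears in Protocol 3.6, 3.8, 3.11 or section 4, or in the SAP. The interview paragraph shows that the authors could state such a limit when they wanted one.

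**2. Can recipients include non-users?** Yes. Protocol 3.8 treats staff tasked with delivery as distinct from other staff. For the first training session it asks for full attendance only from those GPs and advanced nurse practitioners who are involved in running the group consultations. Protocol 3.7 gives dashboard review to one healthcare assistant per practice, and staffs each group consultation with one facilitator and one clinician. Professionals outside these roles still receive the email.

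**3. Could non-users' replies be set aside?** Not by anything described. Protocol 3.7 describes the 10 standard items. Neither document mentions an exposure or role item, a users-only analysis set or a denominator.

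**4. Does the SAP repair this?** No. It has no SUS analysis. The objective numbering in the table in SAP 7.2 runs from 2 to 4, which leaves a gap where protocol objective 3 would stand.

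**5. How large could the effect be?** Let f be the share of respondents who are non-users.

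- Pooled mean = (1 − f) × user mean + f × non-user mean
- Shift from the user mean = f × (non-user mean − user mean)

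Both inputs are assumptions; neither is in the documents. In absolute size, in points on the 0–100 scale:

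| Non-user share f | Gap of 10 points | Gap of 20 points |
|---|---|---|
| 0% | 0 | 0 |
| 10% | 0.10 × 10 = 1 | 0.10 × 20 = 2 |
| 50% | 0.50 × 10 = 5 | 0.50 × 20 = 10 |

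The sign depends on whether non-users rate the service lower or higher than users, which the documents do not tell us.

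**The case against.** The strongest reply is that this is a descriptive feasibility survey with no SUS threshold, so no stated decision turns on a few points. People who never touched the service may simply ignore the email. HCP views are also gathered in 10 interviews confined to deliverers. All of that is fair, and it limits the weight of the point. It does not remove it: the interviews serve the acceptability objective, and the SUS alone serves usability among HCPs.

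Several stronger readings are tempting, but the documents do not support them:

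- **That the score will be contaminated.** This needs non-users who reply, and the documents give neither number.
- **That the score will be understated by a definite amount.** Assuming means of 75 for users and 50 for non-users, a 25% non-user share gives 0.75 × 75 + 0.25 × 50 = 68.75 and a 60% share gives 0.40 × 75 + 0.60 × 50 = 60.0, shortfalls of 6.25 and 15 points. Every input there is invented, and the direction could reverse.
- **That staff with 15 minutes of training are non-users.** Protocol 3.8 addresses that advice to people who will cover for absent colleagues. They are potential users.
- **That non-users' replies could never be removed.** Protocol 3.7 describes the instrument, not the whole layout of the online survey. Silence about a role item does not show that there will be none.
- **That administrative staff who deliver the service are left out.** Protocol 3.7 lets administrative staff run onboarding, and then calls whoever runs it an HCP. The wording is loose enough to include them, although it should say so.
- **That the planned response rate is meaningless.** Neither document plans one.

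It can also be said that the SAP leaves no SUS score to bias. That is a further gap in the same objective and no defence of the mailing rule, because the protocol still lists the objective as primary and promises descriptive reporting of all outcomes.

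**Conclusion.** The point holds as a risk that the plan permits. As written, the mailing rule reaches staff who did not use Fresh Start, and no described item or analysis set would separate their replies from users' replies in the sole measure of protocol primary objective 3. Whether mixing occurs, how much and in which direction cannot be settled from the documents. The 1 to 10 point range rests wholly on an assumed 10% to 50% non-user share and an assumed gap of 10 to 20 points, and it falls to 0 if only users answer. No stated threshold or decision is shown to change. The case for acting is that the repair is small and is easiest before the single survey goes out.

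**What to change.** In Protocol 3.7, do one of the following:

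- Limit the SUS to staff, expressly including administrative staff, who delivered or used at least one Fresh Start component: patient search, outreach, onboarding, dashboard review or escalation, video group consultations, or the 12-week review. The documents name no ready-made list of such staff, so each practice would compile one from its role assignments.
- Keep the wide mailing and add one opening item on role and components used.

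In either case, report the score in confirmed users, with the numbers invited, exposed and responding.

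In the SAP, add the HCP usability objective with a users-only SUS summary, or document that the objective was removed and why. A change to the protocol alone would leave the score without an analysis plan.

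The cost is a sentence or two of protocol text, at most one survey item and a short SAP entry. No patient procedure changes. The downside is fewer scored responses.
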